2. STUDY OBJECTIVES AND ENDPOINTS

2.1. Objectives

2.1.1. Primary Objective

The primary objective of this study is to determine the confirmed ORR with vidutolimod in combination with cemiplimab.

2.1.2. Secondary Objectives

The secondary objectives of the study are to:

- Evaluate the safety and tolerability of vidutolimod administered by IT injection in combination with cemiplimab
- Evaluate the efficacy of vidutolimod in combination with cemiplimab

2.1.3. Exploratory Objectives

The exploratory objectives of this study are to:

- Evaluate the effect of vidutolimod in combination with cemiplimab on injected and noninjected target lesions
- To demonstrate treatment induced immune effects consistent with vidutolimod mechanism of action, including TLR9 signaling, increase in pDC activation, corresponding increase in CD8 T cell tumor infiltration, and activation status

2.2. Endpoints

2.2.1. Primary Endpoint

The primary endpoint is ORR, defined as the proportion of subjects with a confirmed objective response of CR or PR based on Response Evaluation Criteria in Solid Tumors version 1.1 (RECIST v1.1).

2.2.2. Secondary Endpoints

The secondary endpoints are as follows:

- AEs, SAEs, and AEs leading to discontinuation or death, and severity of AEs as assessed by the National Cancer Institute Common Terminology Criteria for Adverse Events Version 5.0 (CTCAE v5.0)
- DOR, defined as the time from date of first documented response (CR or PR) to date of documented PD, based on RECIST v1.1
- Response in injected and noninjected target lesions per RECIST v1.1
- PFS, defined as the time from date of first dose of study treatment to date of documented PD based on RECIST v1.1 or death, whichever occurs first

- Overall survival (OS), defined as the time from date of first dose of study treatment to date of death

2.2.3. Exploratory Endpoints

The exploratory endpoints of the study are as follows:

- Baseline and post-treatment changes in downstream targets of TLR9 signaling (serum CXCL10), other peripheral blood biomarkers related to pDC activation, type I interferon and effector T cell activation and explore association with clinical outcomes.
- Baseline and post-treatment changes in tumor CD8 T cell density, activation and/or proliferation status and tumor inflammatory gene expression (including IFN-gamma, Golgi gene expression signature).

3. INVESTIGATIONAL PLAN

3.1. Overall Study Design

This is a multicenter, open-label, Phase 2 clinical study of vidutolimod administered by IT injection in combination with cemiplimab IV in subjects with selected types of advanced or metastatic cancer with or without prior PD-1-blocking antibody treatment, as follows:

- Cohorts A1 and A2: Subjects with metastatic or locally and/or regionally advanced unresectable CSCC:
 - **Cohort A1:** Subjects who had not received prior systemic therapy for CSCC and who are not eligible for curative radiation
 - **Cohort A2:** Subjects who have progressed while receiving a PD-1-blocking antibody or within 12 weeks of discontinuation
- Cohorts B1 and B2: Subjects with metastatic or locally and/or regionally advanced unresectable MCC:
 - **Cohort B1:** Subjects who had not received prior systemic therapy for MCC
 - **Cohort B2:** Subjects who have progressed while receiving a PD-1-blocking antibody or within 12 weeks of discontinuation
- Cohorts C1 and C2: Previously treated subjects with advanced or metastatic TNBC. Patients must have previously received treatment with sacituzumab govitecan (all TNBC patients), with trastuzumab deruxtecan (HER2-low patients) and with PARP inhibitor (for BRCA) patients:
 - **Cohort C1:** Subjects who had not received prior therapy with immune checkpoint inhibitors (iCPIs)
 - **Cohort C2:** Subjects who have progressed while receiving a PD-1-blocking antibody or within 12 weeks of discontinuation
- **Cohort D:** Subjects with newly diagnosed metastatic or locally and/or regionally advanced unresectable basal cell carcinoma (BCC) who have not received prior hedgehog pathway inhibitor therapy or prior anti-PD-1/PD-L1 therapy and who do not wish to receive or who are not candidates for a hedgehog inhibitor.
- **Cohort E (not conducted in Europe):** Advanced non-small cell lung cancer (NSCLC) subjects (locally advanced who are not candidates for surgical resection or definitive chemoradiation or metastatic) whose tumors have high PD-L1 expression (tumor proportion score [TPS] $\geq 50\%$) based on a prior PD-L1 result as determined by CAP/CLIA (or equivalently licensed) lab, with no EGFR, ALK, or ROS1 aberrations, and who have not received prior anti-PD-1/PD-L1 therapy and are amenable to IT therapy and do not wish to receive chemotherapy.
- **Cohort F:** R/M OPSCC subjects with HPV-positive, PD-L1 CPS score ≥ 1 disease who have not received prior systemic therapy for R/M disease. HPV-positive status, based on a prior result, must be established in a surgical specimen or a core biopsy

specimen from any site of OPSCC (primary site, nodal site, and/or distant metastatic site, either at time of diagnosis or later) in a CAP/CLIA (or equivalently licensed) lab, as follows:

For subjects with documented history of oropharynx primary disease, either of the following will be accepted as evidence of HPV-positive OPSCC: positive p16 immunohistochemistry (IHC) or positive HPV DNA or RNA in situ hybridization (ISH).

For subjects with HNSCC of unknown primary, positive HPV DNA or RNA ISH is required as evidence of HPV-positive disease.

PD-L1 expression (CPS ≥ 1) is based on a prior PD-L1 result as determined by CAP/CLIA (or equivalently licensed) lab.

Vidutolimod 10 mg will be administered weekly for 7 doses, after which it will be administered Q3W until the subject meets a condition for discontinuation of study treatment. The first dose of vidutolimod may be administered SC or by IT injection, at the discretion of the Investigator; all subsequent doses are planned to be administered IT. The initial 7 vidutolimod doses, administered on a weekly schedule, must be completed before moving on to the Q3W vidutolimod dosing schedule.

The PD-1-blocking antibody administered in this study is cemiplimab. Treatment with cemiplimab will be administered IV infusion over 30 minutes (± 10 minutes) at Week 1 Day 1 (W1D1) and Q3W thereafter. Cemiplimab administration will occur after vidutolimod administration.

All subjects will receive vidutolimod and cemiplimab according to the treatment schedule up to 2 years or until a reason for treatment discontinuation is reached.

Disease status will be assessed by computed tomography (CT) or magnetic resonance imaging (MRI) and other appropriate measures beginning predose at Week 10 Day 1 (W10D1) and will be repeated every 9 weeks (e.g. W19D1, W28D1, etc.) while the subject is on treatment. All scans should be performed at least 2 weeks after the previous vidutolimod IT injection to prevent detection of injection-related pseudoprogression. Imaging should not be delayed for delays in treatment.

Objective responses will be assessed by the Investigator according to RECIST v1.1.

[figure not shown]
Subjects who discontinue study treatment should complete the end of treatment (EOT) visit. AEs and concomitant medications data will be collected until 100 days after the last dose of study drug (vidutolimod or cemiplimab) or until an alternative anticancer treatment is initiated, whichever occurs first, including at a 100-day safety follow-up visit.

Subjects who are posttreatment but have not met criteria for study discontinuation should remain on study for posttreatment follow-up (PTFU), which includes disease assessments every 3 months until discontinuation. Long-term survival follow-up (LTSFU) will be conducted every 3 months after the EOT visit or the last disease assessment date in PTFU.

At the end of the treatment period (2 years), the Sponsor will not continue to provide supplied study treatment to subjects/investigators unless the Sponsor chooses to extend the study. The

investigator should ensure that the subjects receive appropriate standard of care to treat the condition under study.

Figure 1: Vidutolimod Study Schema

Abbreviations: 100DFU = 100-Day Follow-up; EOT = end of treatment; LTSFU = long-term survival follow-up; IT = intratumoral; PD-1 = programmed cell death protein 1; PTFU = posttreatment follow-up; Q3W = every 3 weeks; Q9W = every 9 weeks; Q12W = every 12 weeks; QW = every week; SC = subcutaneous.

Note: The first dose of vidutolimod may be administered by SC or IT injection, per Investigator discretion. All subsequent doses of vidutolimod are planned to be administered IT.

3.2. Treatment Discontinuation

Study treatment should continue until 1 of the following occurs:

- Unacceptable AE that precludes further study treatment (see Section 4.1.1.5.4 and Section 4.1.2.2)
- 2 years of study treatment
- PD per RECIST v1.1; continuation of treatment through suspected pseudoprogression is permitted as described in Section 3.2.1
- Upon request of the Sponsor or regulatory agency
- Clinical disease progression
- If medically necessary in the opinion of the Investigator
- Subject withdraws consent for treatment (Note: A subject who withdraws consent for additional study treatment and procedures but not for antitumor response will continue to be followed.)
- Subject becomes pregnant or begins breastfeeding
- Subject is lost to follow-up (at least 3 documented attempts to contact the subject)
- Death
- End of clinical trial

Subjects who permanently discontinue treatment with cemiplimab because of immune-mediated AEs (imAEs) must also permanently discontinue treatment with vidutolimod.

If a subject achieves and maintains a confirmed CR by Investigator review, treatment with vidutolimod or the combination of vidutolimod and cemiplimab may be discontinued at the Investigator's discretion once they meet both of the following criteria:

- Subject has been treated with both study drugs for at least 24 weeks
- Subject has received at least 3 doses of both study drugs beyond the date of the initial CR

Subjects who discontinue study treatment should undergo the EOT assessments. Subjects who discontinue study treatment for reasons other than disease progression (per RECIST v1.1 by Investigator, or clinical PD per Investigator) should remain on study for PTFU and receive disease assessments according to the Schedule of Assessments ([Table 1](#)). Long-term survival follow-up will be conducted every 3 months after the EOT visit or the last disease assessment date in PTFU.

3.2.1. Treatment Beyond Progression

Subjects with a single tumor assessment of PD (per RECIST v1.1) may continue treatment until the next tumor assessment, at the discretion of the investigator based on the clinical state of the patient after communication with the Sponsor, if the following conditions are met:

- The subject has no decline in performance status (as defined by ECOG)
- The subject has absence of clinical symptoms or signs indicating clinically significant disease progression; absence of rapid disease progression or threat to vital organs or critical anatomical sites (eg, central nervous system metastasis, respiratory failure due to tumor compression, spinal cord compression) requiring urgent alternative medical intervention
- The subject has no significant, unacceptable or irreversible toxicities related to study treatments, including any AE(s) that would require permanent discontinuation of either vidutolimod or cemiplimab
- The subject provides consent prior to resuming treatment; this will be done by repeating the informed consent process that was conducted prior to initial study enrollment, with the subject signing (or having their legally authorized representative sign, as appropriate) the current version of the informed consent form (ICF)

Subjects will continue on the same schedule of assessments, with treatment continuing according to the next scheduled clinic visit (ie, treatments missed outside of the visit window will not be made up). As a general rule, if further progression occurs after study treatment is resumed ($\geq 20\%$ increase in tumor measurements by RECIST 1.1 criteria, using the initial progression scan as the comparator, and/or development of new lesions) that study drugs will be discontinued.

Treatment beyond the second progression may be allowed in selected cases after communication with the Sponsor (e.g., progression of lesion(s) that has(have) not been injected at the time of documented progression if the plan to inject the progressing lesion(s) after documented progression).

3.3. Study Withdrawal

Subjects may withdraw from the study at any time and without penalty or loss of future medical care, or any other benefits to which they are otherwise entitled. Subjects will be withdrawn from the study for any of the following reasons:

- Subject withdraws consent for the study
- Subject lost to follow-up
- Death
- End of clinical trial

For subjects who withdraw consent from overall study participation (not only study treatment) will not have the EOT visit, safety follow-up visits, or further evaluations performed.

3.4. End of Clinical Trial

The definition for End of Study (Trial) is the date of global last subject's last visit (100 days ± 7 days after the last dose of study drug: vidutolimod or cemiplimab), or the date of withdrawal from the study, or lost to follow-up (i.e., the study subject can no longer be contacted by the investigator) whichever comes first. The sponsor has the right to terminate the study at any time. All data collection will cease in all subjects when the end of the clinical trial is reached.

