- m. Clinical laboratory assessments may be performed up to 72 hours before vidutolimod injection. When clinical laboratory assessments are done the same day as vidutolimod injection, vital signs should be performed prior to collection of clinical laboratory tests. Refer to Section 6.1.12 for Clinical Laboratory Assessments.

Note: For WOCBP, a serum pregnancy test and FSH are completed at Screening and W1D1. WOCBP must have a negative serum or urine pregnancy test (minimum sensitivity 25 IU/L or equivalent units of human chorionic gonadotropin) within 24 hours prior to the start of study treatment. An extension up to 72 hours prior to the start of study treatment is permissible in situations where results cannot be obtained within the standard 24-hour window. Serum or urine pregnancy tests are also to be completed prior to vidutolimod injection on W4D1, W7D1, and Q3W thereafter and EOT. Refer to Section 6.1.13 for pregnancy testing. An additional pregnancy test must be conducted at the end of the relevant systemic exposure, ie, 16-18 weeks after last study dose treatment. A urine test conducted at home and communicated to the investigator by phone would be acceptable. Pregnancy testing should be performed in women having a bilateral tubal ligation. A follicle stimulating hormone test is required to confirm menopause in women with less than 12 months of amenorrhea. If fertility is unclear and a menstrual cycle cannot be confirmed before the first dose of study treatment (W1D1), subject should be considered of childbearing potential and applicable pregnancy tests completed.

Note: Coagulation samples (PT, INR, and PTT) are to be collected prior to the W1D1 visit. Subsequent results are to be reviewed before every vidutolimod injection beginning at W7D1 and continuing Q3W thereafter.

Note: At Screening, subjects assessed as at risk for adrenal insufficiency should undergo diagnostic tests for ACTH and morning cortisol, and/or high-dose ACTH stimulation test (preferred testing method), if clinically indicated, via local laboratory.

n. Serum samples are to be collected at the following time points:

- Within 2 hours before vidutolimod injection on W1D1, W3D1, W4D1, W7D1
- 4 hours (\pm 30 minutes) after the start time of the vidutolimod injection on W1D1, W4D1, W7D1
- 2 hours (\pm 30 minutes) after the start time of the vidutolimod injection on W3D1

Refer to Section 6.3.1. Collection of Blood for Translational Biomarker Analyses.

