6.1.13. Pregnancy Testing

Pregnancy testing will be performed on WOCBP at the time points specified in the Schedule of Assessments ([Table 1](#)). A serum pregnancy test is required during Screening. A serum or urine pregnancy test will be completed for time points after Screening.

A WOCBP must have a negative serum or urine pregnancy test (minimum sensitivity 25 IU/L or equivalent units of human chorionic gonadotropin) within 24 hours prior to the start of study treatment. An extension up to 72 hours prior to the start of study treatment is permissible in situations where results cannot be obtained within the standard 24-hour window. A final pregnancy test must be conducted at the end of relevant systemic exposure ie, 16 to 18 weeks after last study dose treatment. A urine test conducted at home and communicated to the investigator by phone would be acceptable. Pregnancy testing should be performed in women having bilateral tubal ligation.

If a urine pregnancy test is positive at any time point, the test must be confirmed with a serum sample. If a serum pregnancy test is required based on a positive urine pregnancy test, serum test results must be confirmed as negative prior to enrollment or subsequent treatment of the subject. If the serum test confirms the subject is pregnant, they must have the EOT visit and the pregnancy must be reported to the Medical Monitor.

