7.3.3. Reporting Pregnancies

Female subjects or the partners of male subjects who become pregnant within 150 days of their last vidutolimod dose will be instructed to notify the Investigator immediately.

If the Investigator learns of a report of pregnancy at any time after the W1D1 visit up to 150 days after the last dose of the study drug, the Investigator must complete and submit a paper Pregnancy Report Form and report the pregnancy to Regeneron within 24 hours of awareness (following the same reporting process outlined in Section 7.3.2).

The Investigator will inform the subject that the Sponsor or its representatives is required to gather information regarding the course and outcome of a pregnancy that has occurred after exposure to a study drug. The progress of the pregnancy must be followed until the outcome of the pregnancy is known (i.e. delivery, elective termination, or spontaneous abortion). If the pregnancy results in the birth of a child, additional follow-up information may be requested.

The Investigator will be asked to obtain follow-up information no later than 2 months after the gestational period to obtain maternal/fetal/neonatal outcome and any other relevant information.

Follow-up information may be requested at additional time points. All study-related contacts involving a known pregnancy should include pregnancy status assessment until pregnancy outcome is known.

Please note that pregnancy in and of itself is not an AE or an SAE. Pregnancy should not be entered into the eCRF as an AE unless the Investigator suspects an interaction between the study drug and the contraceptive method. Additionally, all information received will be assessed for any AEs and SAEs and processed per study guidelines. If the subject is discontinued because of pregnancy, pregnancy will be documented as the reason for study discontinuation. Spontaneous abortions and stillbirths will be reported as SAEs.

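### Section 3.4 stops all data collection at day 93–107 after the last dose, before the mandatory final pregnancy test (day 112–126) and the end of pregnancy reporting (day 150); separately, 7.3.3 counts the notification instruction from vidutolimod alone

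*Protocol*

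**What the plan says.** Protocol section 3.4 defines the end of trial as the global last subject's last visit, 100 ± 7 days after the last dose of vidutolimod or cemiplimab. Withdrawal, loss to follow-up or sponsor termination can bring it forward. The section closes with: "All data collection will cease in all subjects when the end of the clinical trial is reached". It lists no exception.

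Other sections set duties that run longer:

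- Section 6.1.13, which applies to women of childbearing potential: "A final pregnancy test must be conducted at the end of relevant systemic exposure ie, 16 to 18 weeks after last study dose treatment". Table 1, footnote m, says the same: "An additional pregnancy test must be conducted at the end of the relevant systemic exposure, ie, 16-18 weeks after last study dose treatment".
- Section 7.3.3 obliges the investigator to report any pregnancy learned of "up to 150 days after the last dose of the study drug", and adds: "The progress of the pregnancy must be followed until the outcome of the pregnancy is known".
- Section 7.3.3 also tells female subjects, or partners of male subjects, to notify the investigator at once if they "become pregnant within 150 days of their last vidutolimod dose".

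The 150-day periods in 7.3.3 therefore start from two different doses. The investigator's duty runs from the last dose of study drug, while the instruction to subjects and partners runs from the last vidutolimod dose. Exclusion criterion 24 also uses 150 days, counted from the last dose of study treatment.

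**The concern.** A site with a subject dosed near the end of the trial has two opposing instructions and no rule for which prevails. If it follows 3.4, it stops before a test that the protocol makes compulsory and before pregnancy reporting and follow-up are complete.

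The notification point is separate and can arise well before the end of the trial. The protocol foresees cemiplimab continuing after vidutolimod has stopped: for complete response (3.2), for vidutolimod toxicity (4.1.1.5.4), and in the separate end-of-treatment visits of Table 1, footnote b. Footnote j duly counts adverse event collection in such subjects from the last cemiplimab dose. The notification instruction does not follow suit, so it can lapse while the subject is still being dosed. Partners of male subjects are the most exposed. They have no scheduled tests, so the investigator can report only what someone tells them.

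What is at stake is pregnancy safety follow-up. Response rate, sample size and the other efficacy analyses are unaffected.

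**Working it through.** The plan states no figure for this gap, so the check is calendar arithmetic on its own day counts.

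**Inputs**

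- End of trial, E = 100 ± 7 = day 93 to 107 after the global last dose (3.4).
- Final pregnancy test: 16 × 7 = day 112 to 18 × 7 = day 126 after the subject's last dose (6.1.13; Table 1, footnote m).
- Investigator reporting: to day 150 after the subject's last dose of study drug (7.3.3).
- Notification: 150 days from the last vidutolimod dose (7.3.3).
- Cemiplimab interval: 21 days (4.1.2).

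**The last-dosed subject.** The test window opens 112 − 107 = 5 to 112 − 93 = 19 days after data collection stops. It closes 126 − 107 = 19 to 126 − 93 = 33 days after the stop. Reporting ends 150 − 107 = 43 to 150 − 93 = 57 days after it.

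**Who else is affected.** A subject last dosed X days before the global last dose is at day X + E when the trial ends. A duty due on day D is missed or cut short if X < D − E.

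| Duty | D | E = 107 | E = 100 | E = 93 |
|---|---|---|---|---|
| Test falls wholly after end of trial | 112 | X < 5 | X < 12 | X < 19 |
| Test window cut short | 126 | X < 19 | X < 26 | X < 33 |
| Reporting window cut short | 150 | X < 43 | X < 50 | X < 57 |

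Subjects who finished treatment earlier than this are not affected by the testing and reporting gaps. Outcome follow-up is a different matter: it is cut for any pregnancy whose outcome is still unknown at end of trial, apart from related serious events.

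**Notification.** Assume the last vidutolimod dose is given at a shared three-weekly visit and is followed by k cemiplimab-only doses. The notification period remaining after the last study drug dose is 150 − 21k days:

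- k = 1: 150 − 21 = 129 days
- k = 4: 150 − 84 = 66 days
- k = 7: 150 − 147 = 3 days
- k = 8: 150 − 168 = −18, so it lapsed 18 days before that dose

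**A long-duration illustration.** Section 3.2 lets a subject with a maintained confirmed complete response stop vidutolimod once treated for at least 24 weeks, if the dose-count condition is also met. Take a last vidutolimod dose at week 24, day 168. Notification ends at day 168 + 150 = 318. Cemiplimab may run to two years, here 104 × 7 = 728 days, which leaves up to 728 − 318 = 410 days (just over 58 weeks) with no instruction in force.

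**The case against.** The best reply is that a specific duty survives a general closing sentence. Where the protocol wants the end of trial to cut an activity off, it generally says so: adverse events (Table 1, footnote c), post-treatment follow-up (6.6), survival follow-up (6.7). The pregnancy provisions carry no such cut-off, and 7.3.3 foresees follow-up until 2 months after the gestational period, which no 100-day endpoint could hold. Pregnancies also go to the sponsor on a paper form, which might be held to lie outside data collection. This reading is reasonable, but 3.4 does not state it, and the paper-form argument does not reach the scheduled test.

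The serious adverse event route covers part of the gap. Section 7.3.3 says: "Spontaneous abortions and stillbirths will be reported as SAEs". Table 8 adds congenital anomaly, and related events stay reportable after participation ends (7.3.2, 7.3.6). That stands. But 7.3.3 does not treat pregnancy in itself as an adverse event, so the test, the pregnancy report, and follow-up of uncomplicated or unrelated pregnancies remain uncovered.

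On notification, treated women have some protection: Table 1 schedules pregnancy tests every 3 weeks and at end of treatment, although footnote m words the on-treatment tests as preceding vidutolimod injection. The investigator's own duty does not lapse. The cemiplimab-only group is also limited, because subjects with metastatic disease whose injectable lesions have all regressed switch to subcutaneous vidutolimod (4.1.1.3.1). All of this narrows the point mainly to partners of male subjects on cemiplimab alone. Consent documents, not available here, may give subjects a better instruction, but that would not correct the protocol's wording.

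Exclusion 25 requires contraception for at least 6 months after the last dose. This lowers the chance of pregnancy but does not resolve either inconsistency.

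**Conclusion.** Both parts hold. As written, 3.4 ends data collection 5–19 days before the final pregnancy test window opens for the last-dosed subject, and 43–57 days before her reporting period ends. The notification instruction in 7.3.3 starts from the wrong dose whenever cemiplimab outlasts vidutolimod, and it has lapsed by the eighth cemiplimab-only dose.

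The practical size is limited. The testing and reporting gaps touch only subjects last dosed within the intervals tabulated above. The documents do not say how many there will be; it may be few or none. Day 93–107 is the scheduled case, and an earlier end would widen the gap. The notification figures assume uninterrupted three-weekly dosing after a shared visit. With no effect on any efficacy analysis, this should be corrected but does not threaten the trial's conclusions.

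**What to change.** In 3.4, add a phrase exempting the final pregnancy test, pregnancy reporting and pregnancy outcome follow-up from the stop on data collection. Moving the end of trial to day 150 would cover the test and the reporting period, but outcome follow-up would still need the exemption, so the exemption alone is simpler.

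In 7.3.3, count the notification instruction from the last dose of either study drug, whichever is later. The 150-day length can stay, since it matches exclusion 24.

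The cost is two phrases and limited extra contact with the last few subjects. The protocol already accepts a home urine test reported by phone. No endpoint, analysis or sample size changes.
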